Colonoscopy is the most accurate method that exists for the early detection and prevention of CRC. Although studies evaluating the effect of screening with this test on CRC-caused mortality in average-risk populations have not yet been published, its implementation is recommended based on the following evidence: 1) studies have demonstrated that colonoscopy with polypectomy reduces the incidence of CRC by 40-90% (27,28); 2) At least two case-control studies suggest that screening by flexible sigmoidoscopy significantly reduces the risk of death from distal CRC (29,30), an effect that lasts for more than 5 years (30) which has enabled extrapolation of its effectiveness to colonoscopy; 3) The prevalence of adenomas in cross-sectional studies of screening by colonoscopy is twice that observed for sigmoidoscopy (18,19,31,32), with colonoscopy also found to be more sensitive than the barium enema or virtual colonoscopy for detecting polyps and CRC (26); 4) Approximately two out of three patients with advanced cancers of the proximal colon do not show neoplasia distal to the splenic flexure, meaning that it would not be detectable in screening by sigmoidoscopy (33,34). This is particularly relevant if one considers that 40% of CRCs are located proximal to the splenic flexure (35).

An additional benefit of colonoscopy every 10 years compared to other screening strategies in an average-risk population is that it allows a long period of protection, which can help improve compliance in the population. It also facilitates diagnosis and treatment in one session, which decreases the risk of the loss of patients to follow-up that occurs with tests that are purely diagnostic.

The primary limiting factors for the use of colonoscopy in screening an average-risk population are its invasive nature, including a possible risk of potentially serious complications such as perforation or post-polypectomy bleeding (1-2 per 2,000 examinations), and a higher cost than other screening methods such as the FOBT test.

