## 6. DEFINITIONS

- *Pragmatic study*: study designed to clarify whether an intervention works under real-life conditions and whether it works in terms that matter to the patient. It is simply concerned with whether the intervention works, not how or why.
- *Target population*: 50-69 year-old individuals with verified address in sanitary card.
- *Invited population*: target population excluding non-contacted individuals.
- *Eligible population*: target population excluding non-contacted and excluded individuals.
- *Participant population*: individuals who returned the FIT test (Group 1) or who completed colonoscopy (Group 2).
- *Screening inclusion data*: data of sending the invitation letter.
- *Incomplete colonoscopy*: colonoscopy in which caecal intubation is not possible. When an incomplete colonoscopy occurs, this examination must be repeated or completed with a CT-colonography.
- *Inadequate colon cleansing*: when less than 90% of colorectal mucosa can be properly evaluated due to the presence of faeces, this examination must be repeated.
- *Non-neoplastic polyp*: hyperplastic, hamartomatous or inflammatory polyps.
- *Non-advanced adenoma*: any tubular adenoma <1 cm and with low-grade dysplasia.
- *Advanced adenoma*: adenoma >1 cm in size, or with high-grade dysplasia, or with villous component (>25%).
- *High-risk adenoma*: 3 or more non-advanced adenomas, or any advanced adenoma.
- *Low-risk adenoma*: 1 or 2 non-advanced adenomas.
- *Non-invasive colorectal cancer*: colorectal carcinoma without submucose invasion (pTis). It includes intramucous carcinoma and intraepithelial carcinoma.
- *Invasive colorectal cancer*: colorectal carcinoma beyond the *muscularis mucosa* (pTNM stages I, II, III and IV).
- *Advanced neoplasia*: colorectal advanced adenoma or cancer.
- *Malignant polyp*: adenoma that harbours an area of carcinoma invading submucose (pT1).
- *Polyposis*: existence of >10 polyps. Depending on the histology, it could be adenomatous, hamartomatous or hyperplastic.
- *Non-neoplastic colorectal diseases*: any non-neoplastic disease detected in the colonoscopy (i.e. haemorrhoids, diverticulosis, angiodyplasia, etc.).

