#### Secondary end points:

1. *Participation, detection rate, diagnostic yield and complication rate at the completion of the first round and at the end of study (10 years)*

Definitions of these four key outcomes are as follows:

- Participation: number of participating individuals (i.e. individuals who completed colonoscopy in the colonoscopy group and individuals who returned the test in the FIT arm) relative to the number of eligible individuals.
- Detection rate: number of true positives relative to the number of participating individuals.
- Diagnostic yield: number of true positives relative to the number of eligible individuals.
- Complication rate: number of major complications (i.e. perforation, postpolypectomy bleeding requiring hospitalization, and cardiovascular/pulmonary complications requiring medical management) relative to the number of participating individuals.

Differences in these four key outcomes between both strategies will be established by logistic regression analysis, adjusted by age, gender and participating centre, and reported as odds ratios (OR) with 95% CI.

*2. Overall survival at the end of study (10 years)*

*3. CRC incidence at the end of study (10 years and 15 years)*

*4. Cost-effectiveness analysis*

Cost-effectiveness will be studied with a Markov's model at the completion of study. Results will be reported in terms of quality-adjusted life years (QALY).

*5. Analysis of factors influencing participation in the study*

Factors associated with participation at the completion of first round and at the end of study (10 years) in each screening strategies will be analysed by logistic regression analysis and results reported as OR with 95% CI. Parameters analysed will include demographics, personal and familial characteristics, socio-economic status, etc.

*6. Number needed to screen to detect a colorectal cancer*

The number needed to screen to detect a CRC will be calculated using the inverse of risk (i.e. the number of participants receiving a given screening modality divided by the number of positive cases in that given modality), with 95% CI computed using the inverse of the binomial standard approximation.

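### The complication rate requires a completed colonoscopy in Group 2 but only a returned FIT in Group 1, so a complication that ends an examination for good can drop out of the colonoscopy arm

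*Combined protocol and SAP*

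**What the plan says.** Protocol section 3.2 makes the serious-complication rate of each strategy a secondary objective, both after the first round and at 10 years.

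SAP section 7, Secondary end points, item 1, gives the numerator as "Complication rate: number of major complications (i.e. perforation, postpolypectomy bleeding requiring hospitalization, and cardiovascular/pulmonary complications requiring medical management". The sentence ends with the denominator: "medical management) relative to the number of participating individuals". The same item defines them as "individuals who completed colonoscopy in the colonoscopy group and individuals who returned the test in the FIT arm", and protocol section 6 repeats the rule: "individuals who returned the FIT test (Group 1) or who completed colonoscopy (Group 2".

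On the analysis, item 1 says: "Differences in these four key outcomes between both strategies will be established by logistic regression analysis". The model is adjusted for age, gender and centre.

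Section 6 defines an incomplete examination as a "colonoscopy in which caecal intubation is not possible" and adds: "When an incomplete colonoscopy occurs, this examination must be repeated or completed with a CT-colonography". Section 4.8 and Phase 2 in section 5.1 describe the same recourse. No separate safety population is defined anywhere.

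**The concern.** In Group 2, entry to the safety denominator depends on finishing the procedure that can cause the harm. In Group 1, entry is settled when the kit is returned, before any work-up colonoscopy takes place. A complication that ends an examination can therefore take a Group 2 person out of the analysis, but cannot take out a Group 1 person who has already returned a FIT.

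This is the plan's safety comparison between the two strategies, and the events are rare. If a few leave one arm because of how the denominator is defined, the odds ratio shifts in favour of colonoscopy for reasons unrelated to safety.

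**Working it through.** The plan states no expected count, power or precision for complications, so there is no figure of its own to reproduce. The check has two parts.

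**1. Who enters the analysis under the written rules**

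- Group 2, examination stopped by a complication before the caecum and never completed: not a participant.
- Group 2, examination stopped but later repeated to completion: a participant.
- Group 2, completed by CT-colonography only: unclear, because the text does not say whether this counts as completed colonoscopy.
- Group 2, event after caecal intubation, or delayed bleeding after a completed examination: a participant, and the event counts.
- Group 1, FIT returned, work-up colonoscopy stopped by a complication: a participant, and the event counts.
- Group 1, crossed over to colonoscopy without returning a FIT (allowed by sections 4.4 and 5): not a participant, whatever happened at the examination.

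The numerator wording does not itself exclude non-participants. The loss arises because logistic regression is fitted to individuals: someone outside the participant set contributes neither a denominator count nor an event.

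**2. Illustrative size**

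Inputs from the documents: 27,749 people per arm and 30% expected overall compliance (section 4.5), and a background complication rate for perforation or "post-polypectomy bleeding (1-2 per 2,000 examinations" (section 2). The number of events lost is not in the documents and is assumed.

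- First examinations in Group 2: n = 27,749 × 0.30 = 8,324.7, about 8,325.
- Expected events: T = 8,324.7 × 1/2,000 = 4.16, to 8,324.7 × 2/2,000 = 8.32.
- Rate if L events and the people who had them are lost: (T − L)/(n − L).
- L = 1, T = 4.16: 3.16/8,323.7 = 0.038%, against 0.050%, a fall of 24%.
- L = 1, T = 8.32: 7.32/8,323.7 = 0.088%, against 0.100%, a fall of 12%.

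In whole events this is 1/8 = 12.5% to 1/4 = 25%, hence roughly 12-25% per lost event.

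The loss can also be expressed as f, the assumed share of complications that stop an examination never completed:

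| f (assumed) | Events lost | Group 2 rate (true 0.050%-0.100%) |
|---|---|---|
| 10% | 0.4-0.8 | 0.045%-0.090% |
| 25% | 1.0-2.1 | 0.0375%-0.075% |
| 50% | 2.1-4.2 | 0.025%-0.050% |

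The relative understatement is about f itself.

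If instead every complication stays in the numerator and only the denominator is limited to completers, the rate is T/(n − L). Even at f = 50% and the higher event rate this is 8.32/(8,324.7 − 4.16) = 0.10005%, practically unchanged from 0.100%. The bias comes from events leaving the numerator, not from the smaller denominator.

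**The case against.** The strongest reply is that the exclusion is inferred. The numerator simply counts major complications, and if all are counted the rate barely moves. That is correct arithmetically, but on that reading some events belong to people outside the denominator, and the stated regression cannot be fitted. The text needs correcting either way.

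The second reply is that few events meet the condition, and this largely stands. Loss requires an event before caecal intubation and no later completion, and the protocol provides for a repeat or CT-colonography. Bleeding after polypectomy need not prevent caecal intubation. A reader might infer that the rule removes the most serious events; the documents do not support that. They also do not show how often a person with a major complication goes on to complete an examination.

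Third, a reader might infer that only the colonoscopy arm can lose events. That is too strong, because Group 1 cross-overs without a FIT are also outside the definition. They are left out because no kit was returned, not because an examination was stopped.

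Fourth, a reader might infer that harm lacks a randomised denominator which detection has through diagnostic yield. Diagnostic yield is per eligible person, and section 6 removes non-contacted and excluded people from that group, so it is not an all-randomised denominator. Section 7 also opens by applying intention-to-screen to the main outcomes, without saying whether complications are among them. What can be said is that item 1 specifies no such version for complications.

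Finally, harm per participant is a legitimate question. It should stay in the plan, but with entry rules that do not depend on the outcome.

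**Conclusion.** The point holds in a limited form. Two sections set different entry rules for the two arms, and under the stated regression a Group 2 complication that ended an examination never completed is not counted. The corresponding event in a Group 1 FIT returner is. For this mechanism the direction is towards understating harm in the colonoscopy arm.

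The size is unknown. The figure of roughly 12-25% per lost event is an illustration resting on these assumptions:

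- The 30% is overall compliance, used here as Group 2 colonoscopy uptake.
- The background rate names only perforation and bleeding, while the endpoint also includes cardiovascular and pulmonary events.
- One first examination is counted per person, while the 10-year endpoint would include surveillance colonoscopies.

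The last two probably make the true event total larger and each lost event a smaller share. If the total doubled, for example, one lost event would be 1/16.6 = 6% to 1/8.3 = 12%. A reader might take the f = 50% row as a forecast that the rate is halved; it is only the upper end of an assumed range, and nothing in the documents supports it as likely.

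This should be changed before the analysis, because it concerns a stated analysis-set rule and not just a missing detail.

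**What to change.** In SAP section 7, Secondary end points, item 1:

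- Define the complication set identically in both arms as everyone who returned a FIT or started any study colonoscopy, completed or not and including cross-overs. Analyse by randomised arm.
- Define the outcome as at least one major complication per person, so that it matches the logistic regression.
- Also report the rate over eligible or all randomised people in each arm as the intention-to-screen comparison.
- Keep the completer-based rate as a sensitivity analysis, and state whether completion by CT-colonography makes someone a participant for that purpose.

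The cost is SAP wording and a little extra analysis. Section 4.8 already requires caecal intubation and immediate complications to be recorded in the endoscopy report, so events that stopped an examination should be identifiable. The colonoscopy rate may turn out less favourable.

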#### **3.2. Secondary objectives**

- To compare diagnostic yield and detection rate of CRC and/or advanced adenomas in each screening strategy at the completion of the first round.
- To compare the participation rate in each screening strategy at the completion of the first round, and identify the factors influencing it (i.e. demographics, personal and familial characteristics, socio-economic status, etc.).
- To compare overall diagnostic yield and detection rate of CRC and/or advanced adenomas in each screening strategy at 10 years.
- To compare the overall adherence rate in each screening strategy at 10 years, and identify the factors influencing it.
- To assess the cost-effectiveness of each screening strategy.
- To assess the rate of serious complications in each screening strategy, both at the completion of the first round and overall at 10 years.
- To compare CRC incidence in each screening strategy at 15 years.

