#### 4.4. Study groups, randomisation, and stratification

Asymptomatic men and women aged 50 to 69 years from each participating Autonomous Region will be identified through the corresponding Community Health Registry (CHR) for enrolment into this study. Randomisation will be carried out prior to invitation, with computer-generated lists in blocks of 4 (block randomisation) from the list of health cards, after having previously grouped individuals by household (specified by street address, floor, and apartment number) (see Processes of selecting and inviting the population to be screened section).

All eligible patients will be randomised (1:1 ratio) to the two study groups:

Group 1: Screening by biennial FIT (latex agglutination, OC-Sensor®, cut-off point: 75 ng Hb/ml, corresponding to 15 µg Hb/g of feces), and colonoscopy (after no more than 1 month) for patients with a positive result. Determination of FIT will be made using a single faecal sample, without dietary restriction or interruption of normal treatment of the individual, although the habitual use (>1 month) or recent use (last 7-15 days) of NSAIDs, aspirin, anti-platelet drugs and anticoagulants will be recorded. The above-mentioned cut-off point was used in the baseline round; in subsequent rounds, we decided to modify the cut-off to 20 µg Hb/g of feces since it is the one accepted in the Spanish population-based CRC screening program.

Group 2: Screening by one-time colonoscopy. The ongoing use (>1 month) or recent use (last 7-15 days) of NSAIDs, aspirin, anti-platelet drugs and anticoagulants will also be recorded.

Individuals in Group 1 or Group 2 who do not agree to the type of testing assigned to them may require receiving the alternative test and must still be followed up in order to carry out efficacy analysis according to the intention to screen analysis. The choice of the alternate test will not be actively offered to individuals invited to the study and, accordingly, COLONPREV is not considered a study of sequential screening test offers.

Information on the long-term status of individuals in Group 1 or Group 2 who do not agree to participate in the study will be obtained through population-based registries at the completion of the trial in order to assess efficacy according to the intention to screen analysis.

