#### 4.5. Sample size calculation

##### Considerations for calculation of the sample

Since there are no study examining the effect of screening with the strategies proposed in our trial on CRC-caused mortality, the calculation of the sample in this case must be based on hypothetical studies of cost-effectiveness that analyse the expected reduction in risk of mortality with biennial FIT or colonoscopy every 10 years. Furthermore, the calculation should be adjusted, when possible, to the local conditions where the strategies are to be implemented. In that sense, it is important to note that no study on this subject have yet been published in Spain.

Recently, the Evaluation and Planning Unit of the Canary Islands Health Service has conducted a study of this type based on real data for sensitivity and specificity of the tests in our setting. For a hypothetical population of 100,000 asymptomatic individuals aged 50, the estimated mortality reduction brought about by FIT is 51% and involves a cost of € 2,101/QALY. For the strategy of colonoscopy, the estimate is a reduction in mortality of 75% at a cost of € 2,188/QALY.

With an alpha risk of 0.025 and a beta risk of 0.10 using one-sided test of proportions, 27,749 subjects are required in each arm of the clinical trial (total: 55,498) accepting a non-inferiority condition if the absolute difference was below 1.6% in the CRC-specific mortality rate at 10 years according to the intention to screen analysis and with an expected overall compliance of 30%.

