#### **4.6. Processes of selecting and inviting the population to be screened**

In each Autonomous Region, randomisation will be done prior to sending the invitation letter (Zelen's design) in order to properly assess the participation in each screening group and perform the intention to screen analysis of the results.

The selection process will be the same as the one used in the Nottingham study (14), in which compliance with the programme reached 60%. Briefly, target population will be identified from the Community Health Registry (CHR) of each Autonomous Region. The CHR is based on the population registry, and includes unique identification for each person, such as name, date of birth, social security number, and contact address, and it is updated regularly to account for population migration, deaths and changes in personal details. This list will be refined using cancer registries or other sources of information (primary care medical records, hospital databases, etc.) in order to eliminate individuals who meet exclusion criteria (i.e. CRC and colorectal adenoma) or who have died. Prior to randomisation, individuals will be clustered by household. With such an approach, it is hoped to ensure that all individuals in one household will be assigned to the same study group.

All individuals will receive an initial, pre-invitation letter by mail (which may be signed by their primary care doctor or an area specialist, or the person responsible for the Autonomous Regions screening programme) with information regarding the relevance of CRC as a health problem, the possibility of preventing it by means of screening, and the impending start up of a pilot programme (**presentation letter**), along with an informative leaflet which explains existing measures for CRC prevention. They will later be sent a second letter (also signed by their primary care doctor or area specialist, or the person responsible for the Autonomous Regions screening programme) in which they are invited to participate in the study (**invitation letter**) and includes an appointment to the Local Screening Office (LSO) and a contact telephone number. In the invitation letter, individuals will also be informed of the screening option that applies to them, the characteristics of the test and its possible adverse effects. This whole process will be performed by the LSO (who may be assisted by staff of the project data manager).

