In patients treated with anti-platelet agents, both for those in Group 1 with a positive FIT test (positive predictive value for colorectal neoplasia greater than 40%) and in Group 2 (positive predictive value of 5-7%), withdrawal or changes in medication will be assessed 7-10 days before testing. However, it is important to note that, according to current scientific recommendations, it is not necessary to discontinue anti-platelet agents to perform a polypectomy. Anti-coagulated patients (dicoumarol) should be changed, when possible, to subcutaneous administration of LMW heparin. Finally, the usefulness of metal clips has been described for the prophylaxis and treatment of post-polypectomy bleeding in at-risk groups, including in anti-coagulated patients.

The American Heart Association does not recommend the use of antibiotics prior to completion of endoscopic procedures (including colonoscopy and polypectomy) for prophylaxis of infectious endocarditis (<http://circ.ahajournals.org/cgi/reprint/CIRCULATIONAHA.106.183095>).

Biopsy of the polyp will be sought before polypectomy, especially for patients in whom it is anticipated that it will be difficult to obtain after the procedure. This measure aims to reduce the number of polyps not histologically studied.

In cases where colon cleansing is not adequate, the colonoscopy will be repeated.

In cases of failure to achieve complete colonoscopy, the procedure will be repeated or a CT-colonography will be offered.

Quality standards will be established for all the above requirements according to the recommendations made by the Quality Assurance Task Group of the National Colorectal Cancer Roundtable (44), which shall be subject to internal auditing during the course of the study. This will be the responsibility of the Quality Committee created specifically for this purpose (see below).

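### Households are grouped before randomisation, but the analysis plan names no household-clustered variance, so the between-arm participation interval is too narrow if co-residents accept or refuse together

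*Combined protocol and SAP*

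**What the plan says.** Section 4.4 randomises 1:1 in blocks of 4 from the health-card list "after having previously grouped individuals by household (specified by street address, floor, and apartment number"). Section 4.6 gives the purpose: "it is hoped to ensure that all individuals in one household will be assigned to the same study group". The household is therefore the intended unit of allocation, although same-arm allocation is expressed as a hope and not as a guarantee.

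Section 3.2 lists as a secondary objective: "To compare the participation rate in each screening strategy at the completion of the first round, and identify the factors influencing it". It also lists a comparison of adherence at 10 years.

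Section 7 (Secondary end points, item 1) sets the between-arm analysis of participation, detection rate, diagnostic yield and complication rate: "Differences in these four key outcomes between both strategies will be established by logistic regression analysis, adjusted by age, gender and participating centre". The separate analysis of participation factors (item 5) is done within each arm; the factors "in each screening strategies will be analysed by logistic regression analysis and results reported as OR with 95% CI". The number needed to screen (item 6) is reported "with 95% CI computed using the inverse of the binomial standard approximation". The survival-type analyses use Kaplan-Meier risks with normal-approximation intervals.

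Neither section 7 nor the sample size section (4.5) mentions household, a robust variance, GEE, a random effect, an intracluster correlation or a design effect.

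**The concern.** When people are allocated in groups, the variance of the between-arm contrast depends on how alike group members are. Ordinary logistic regression treats every individual as independent. A centre term absorbs differences between centres, not the likeness of two people at the same address. Participation is the outcome most exposed. Co-residents intended for one arm are invited to the same test, and partners may well decide together.

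What is at stake is the stated precision of a secondary comparison: a nominal 95% interval for the participation odds ratio would cover less than 95%.

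The within-arm factor analysis is not a randomised contrast, but the same omission affects it, and the direction depends on the covariate. Standard errors would be too small for a covariate shared by the household, such as socio-economic status, and too large for one that differs within couples, such as sex.

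**Working it through.** **Plan's own figure.** The plan states no interval width, correlation or design effect for participation, so there is nothing to reproduce. The 27,749 per arm in section 4.5 is used only as an input.

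**Inputs from the documents**
- n = 27,749 per arm (section 4.5). This is an upper bound here, because participation is counted among eligible individuals.
- p = 0.30, the expected overall compliance in section 4.5.
- q = 0.05-0.07, the predictive value for colorectal neoplasia quoted for Group 2 in section 4.8, used here as the yield among those examined. It is a one-arm figure.

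**Assumptions, not in the documents**
- s, the share of individuals in a household pair: 0.4-0.6, with 0.2 as a low case.
- ICC, the within-household correlation of participation: 0.3-0.7.
- Every pair is allocated to one arm (relaxed below).

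**Formulas for the between-arm comparison of participation**
- DEFF = 1 + s × ICC
- Naive width relative to correct width = 1/√DEFF
- Coverage of the naive interval = 2Φ(1.96/√DEFF) − 1
- Risk-difference half-width = 1.96 × √(2 × 0.30 × 0.70/27,749 × DEFF)
- Odds-ratio limit factor = exp(1.96 × √(2/(27,749 × 0.21) × DEFF))

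| s | ICC | DEFF | Naive/correct width | Coverage | Correct half-width (points) | OR factor |
|---|---|---|---|---|---|---|
| any | 0 | 1.00 | 1.000 | 95.0% | 0.76 | 1.037 |
| 0.2 | 0.3 | 1.06 | 0.971 | 94.3% | 0.79 | 1.038 |
| 0.2 | 0.7 | 1.14 | 0.937 | 93.4% | 0.81 | 1.040 |
| 0.4 | 0.3 | 1.12 | 0.945 | 93.6% | 0.81 | 1.039 |
| 0.6 | 0.7 | 1.42 | 0.839 | 90.0% | 0.91 | 1.044 |

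**Does covariate adjustment remove the effect?** The planned model (age, sex, 8 centres) was simulated, 400 trials per scenario.
- s = 0.5, ICC = 0.5: household-robust SE 0.0207 against model SE 0.0185, ratio 1.118 (theory √1.25 = 1.118). Coverage was 90.8% unclustered and 93.8% clustered.
- s = 0.7, ICC = 0.7: ratio 1.220; coverage 90.5% and 95.5%.
- s = 0.5, ICC = 0: ratio 1.000; coverage 95.3% for both.

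Adjustment does not remove the effect, and the effect vanishes when the correlation is zero.

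**Split households.** If a share c of pairs lands in one arm, DEFF = 1 + s × ICC × (2c − 1). At c = 0.9 the range becomes 1 + 0.12 × 0.8 = 1.10 to 1 + 0.42 × 0.8 = 1.34. At c = 0.5 there is no inflation.

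**Other outcomes**
- Diagnostic yield, with findings independent given participation: yield ICC = [(p² + ICC × p(1 − p))q² − (pq)²]/[pq(1 − pq)].
  - q = 0.05, ICC = 0.3: (0.153 × 0.0025 − 0.000225)/0.014775 = 0.011, so DEFF = 1 + 0.4 × 0.011 = 1.004.
  - q = 0.07, ICC = 0.7: (0.237 × 0.0049 − 0.000441)/0.020559 = 0.035, so DEFF = 1 + 0.6 × 0.035 = 1.021. The interval is at most 1% too narrow.
- CRC mortality, correlation assumed no more than 0.01: DEFF at most 1 + 0.6 × 0.01 = 1.006.
- Detection rate: its denominator is participants, so under the same independence assumption there is no inflation. Complications were not computed.

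**Within-arm factors.** Simulated with 1,500 runs, 27,749 per arm, 30% uptake and opposite-sex pairs, at (s, ICC) = (0.4, 0.3) and (0.6, 0.7).
- Sex: naive/true SE 1.07 and 1.30; coverage 96.5% and 99.5%.
- Household-shared binary covariate: naive/true SE 0.95 and 0.86; coverage 93.5% and 90.7%.

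**The case against.** The strongest objection is that little changes in practice. Even the worst case adds about 0.15 percentage points to the half-width (0.91 − 0.76), and the plan sets no margin or powered hypothesis for participation. Only a difference very close to the significance boundary would be read differently. This stands, and it limits the weight of the point.

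The size also rests on assumed inputs: the documents give no household composition and no correlation, and the 90.0% figure needs both assumptions at their upper end. That stands too. The direction needs only positive correlation and same-arm allocation.

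Same-arm allocation is itself uncertain. Section 4.4 does not say whether a card or a household fills a slot in a block of 4. If cards did, in household order, two partners in one block would share an arm with probability 1/3, and the naive interval would be too wide. Section 4.6 makes the same-arm reading the more likely one. A household-clustered variance is valid either way, so this argues for the fix and for reporting split households.

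Finally, silence about variance does not exclude a robust one. But the plan names a standard model with no household term, and a reader would run it with default standard errors.

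**Conclusion.** The concern holds, conditionally. With households kept together and uptake positively correlated within them, the between-arm participation interval run as written covers less than its nominal 95%: about 93.6% to 90.0% under the main assumptions, and 94.3% to 93.4% if only 20% of individuals are in pairs. If some households are split, the shortfall is smaller. The same applies to 10-year adherence to the extent that it is correlated within households.

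Odds ratios and risk differences are not biased by this. Diagnostic yield is barely affected, and the primary mortality comparison not materially so. The within-arm factor intervals can err in either direction. The point is worth correcting because it concerns the error bars on a stated secondary objective and is cheap to fix; it does not threaten the trial's main conclusion. Confidence in the direction is good; confidence in the size is moderate at best, because it depends on inputs that the documents do not supply.

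**What to change.** Add to section 7 that the logistic models for the four key outcomes, and the within-arm models of participation factors, use household-clustered variance (sandwich, or GEE with household as the cluster), with household defined by the grouping made for randomisation. No correlation needs to be assumed; if there is none, the intervals are essentially unchanged. For the 10-year risk differences and ratios, a household-level robust or bootstrap variance is optional for consistency and will change little. Report the number of households with members in both arms.

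The cost is one sentence and a household identifier in the analysis data. The data-recording paragraph of section 5.2 does not list such an identifier, so it would have to be linked from the randomisation grouping. Section 8 dates the first-round interim analysis to July 2011, so first-round participation may need its interval recalculated. The participation interval would widen slightly; some within-arm intervals, such as that for sex, may narrow.
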